Milestone 3: We will calculate the association between frequency of cannabis use (days) and total quantity of cannabis consumed per week based on participants' EMA data concerning quantity of cannabis use.

If the proposed R21 milestones are met, we will complete the following specific aims during the R33 phase:

R33 Aim 1: Assess the impact of reduced frequency and quantity of cannabis use on functioning.

Hypothesis 1a: Decreased cannabis use will be associated with significant improvements in mental health symptoms, self-efficacy, physical activity, and health-related quality of life.

Hypothesis 1b: Decreased cannabis use will be associated with significant improvements in working memory, impulsivity, and drugged driving.

R33 Supplementary Aim: Explore momentary (e.g., craving, sleep) and between-person factors (e.g., sex, baseline use) that might moderate the association between cannabis use and functioning.

Expected Outcomes: The proposed research will be the first study to systematically assess the impact of reduced frequency and quantity of cannabis use on functioning. As such, these findings will directly inform ongoing efforts to include reductions in illicit drug use as a valid, clinically-meaningful outcome measure in clinical trials of pharmacotherapies for the treatment of CUD and other substance use disorders (Tiffany et al., 2011; Donovan et al., 2011).

A. SIGNIFICANCE

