C.6.4. Cohort 2: Further Protocol Refinement. Once the protocol and/or reinforcement schedule have been modified based on information learned from the first cohort, we will administer the revised mobile CM for cannabis protocol to a second cohort of heavy cannabis users ($n=6$) and repeat the evaluative measures described above. Any additional modifications needed to improve adherence, acceptability, or efficacy of the mobile CM for cannabis protocol will be implemented at this time. We have found this second small cohort particularly helpful in previous treatment development studies, as it allows for careful evaluation of changes in procedures and reinforcement schedules.

C.6.5. Cohort 3: Milestone Assessment. Once the EMA protocol and CM reinforcement schedule have been finalized based on information learned from cohort 2, we will administer the final version of the

protocol to a third cohort ($n=6$) to determine if our first two milestones have been met. Our first milestone will be to demonstrate that a majority (i.e., 4/6) of cohort 3 participants will be adherent to the study protocol and rate the study procedures as acceptable. Protocol adherence will be defined as completing the baseline assessment, 8-week follow-up assessment, and 1 or more EMA assessments per day (total ≥ 56) for the duration of the 8-week EMA protocol. Acceptability will be assessed with a questionnaire specifically designed for this study. Our second milestone will be to demonstrate that we have identified a reinforcement schedule that reliably produces $\geq 50\%$ reductions in frequency and quantity of cannabis use in at least half of the participants in cohort 3 (i.e., 3/6). By aiming to reliably produce clinically meaningful reductions in frequency and quantity of cannabis use in at least half of the participants, we will maximize our ability to study the impact of reduced cannabis use on key functional outcomes during the R33 phase of the project. To evaluate if this milestone has been met, we will calculate the percentage reduction in bioverified abstinent days and overall cannabis quantity by comparing the *ad lib* monitoring period to the mobile CM period.

C.7. Association between Frequency of Use and Total Amount of Cannabis Consumed (R21 Aim 2)

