| | | 2 | \$2.50 | No | | | | | |
| 54 | 1 | \$2.50 | Yes | | \$49.00 | | \$54.00 | \$1520.00 | |
| | | 2 | \$2.50 | Yes | | | | | |
| | 55 | 1 | \$2.50 | No | \$50.00 | | \$55.00 | \$1575.00 | |
| | | 2 | \$2.50 | No | | | | | |
| 56 | 1 | \$2.50 | No | | \$51.00 | | \$56.00 | \$1631.00 | |
| | 2 | \$2.50 | No | | | | | | |

only asked to respond to two daily alarms (instead of three). Note, this decreases the potential amount of money earned.

Seventy-two participants will be randomized using a 2:1 allocation ratio to either the Reduced Use

Condition (n = 48) or a Control Condition (n = 24). Inclusion of a control group will allow clear inferences to be drawn regarding the effects of reduced cannabis use on functional outcomes. Study participation will entail completion of the baseline assessment, completion of the 8-week EMA study, and completion of the 8-week follow-up assessment.

D.2. R33 Inclusion/Exclusion Criteria and Recruitment

Timeline

The final inclusion/exclusion criteria for the R33 phase of project will be identical to the R21 inclusion/exclusion criteria with one exception: Participants who are found to meet criteria for bio-verified sustained abstinence (i.e., all of their saliva tests are negative during the 6-week experimental phase of the study) will be excluded from the statistical analyses to ensure that there is an upper limit on reduced use. Thus, we will exclude any participants who achieve sustained abstinence to ensure that any improvements in functioning observed among participants in the experimental condition are not being driven by inclusion of a subset of participants who achieve sustained abstinence. Please also note that we can exclude up to 12 of the 72 enrolled participants from the statistical analyses (remaining N = 60) and still be adequately powered to conduct all of the proposed analyses.

[figure not shown]
D.3. Diagnostic Reliability and Training of Clinical Interviewers

Interviewers will be trained to conduct the interviews using our standardized laboratory procedures, including rating videotaped interviews and participation in ongoing weekly supervision. These procedures have produced consistently high interrater reliability, with Fleiss' kappa values ranging from .92-.94 in previous studies (Kimbrel, Newins et al., 2017; Kimbrel, Calhoun et al., 2014).

D.4. Participant Reimbursement

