In addition to the compensation that participants will receive from the CM procedures, participants will also receive \$75 for completion of the baseline assessment, \$25 for the post *ad lib* period urine testing, \$150 for the 8-week follow-up, and \$400 for the EMA study (\$50 per week). They will also be eligible to receive a \$25 bonus per week for not missing more than 1 EMA alarm per day, and a \$50 bonus for returning their equipment on time. These procedures have worked well (high compliance and equipment return rates) in previous studies (Carpenter et al., 2015; Hertzberg et al., 2013; Beckham, Calhoun et al., 2013; Dennis et al., 2016; Volz et al., 2014). Participants may also receive \$20 for successfully recruiting another participant in his/her/their social network.

Figure 2. R33 Study Design & Participant Flow

D.5. Description and Timing of In-Person Assessments

Table 2 describes the laboratory and self-report assessments that will be collected at the baseline and 8-week follow-up assessments as well as their administration schedule. Whenever possible, we have selected Common Data Elements from the PhenX Toolkit (Hamilton et al., 2011) to maximize the impact of the proposed research. We have also elected to use brief measures when possible to reduce burden. Whenever possible, participants will complete questionnaires remotely using Duke's instance of RedCap.

D.6. EMA and CM Procedures

EMA addresses the limitations of traditional assessment techniques by (a) repeatedly assessing participants in their normal daily environment, which enhances ecological validity; (b) assessing experiences and behaviors at the time they occur, which minimizes memory biases associated with retrospective recall; and (c) allowing for examination of the context of participants' experiences.

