to stress, trauma, and coping strategies. Participants will be informed about these new study procedures verbally, and the study team member who informs them will provide a note-to-fil indicating so. Participants can refuse to complete these measures. We will ask ongoing participants to complete these measures at their next study visit or follow-up session. When study enrollment begins again, participants will complete these measures at the screening session. We are adding the CAIR Pandemic Impact Questionnaire (Lang, 2020; https://www.nlm.nih.gov/dr2/CAIR-PIQ_scoring.pdf), and another measure, COVID Core Questions, with variables of interest. If a participant endorses any item marked with an asterisk on the COVID Core Questions measure, we will ask them to complete a PTSD Checklist 5 related to that specific event. Finally, we have added a measure designed to evaluate participants' satisfaction with remote study procedures.

E. DATA ANALYSIS PLAN

Multilevel modeling (MLM) will be used to analyze the EMA data. MLM is a technique for analyzing repeated observations of data across multiple individuals. Unlike repeated-measures ANOVA, MLM can incorporate time-varying (Level-1) and time-invariant (Level-2) predictors. MLM can also accommodate imbalanced data and unequal variances. The main conclusions drawn from this study will be based on the pre-specified hypotheses, which will be tested with two-sided statistical tests at an alpha of .05. Analyses will be performed with SAS for Windows (Version 9: SAS Institute, Cary, NC).

E.1. Missing Data.

Although we do not anticipate much missing baseline data, we do anticipate missing values in the EMA data. MLM procedures, which will be used to analyze H_{1A}, H_{1B}, and the supplementary aim, are based on maximum likelihood estimation and use all available data. As such, MLM can accommodate data missing at random. Missing data will be examined to determine whether missingness is random or systematically associated with baseline variables. Those baseline parameters associated with missingness will be covaried. If data are suspected to be missing not at random (i.e., only certain values are likely to be missing), multiple imputation will be used to analyze non-random patterns of missing EMA data (Schafer & Graham, 2002).

E.2. Electronic Diary Compliance and EMA Data Reduction.

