During the 8-week EMA data collection, we will calculate the percentage of responses recorded within 5 minutes of the random prompts. We will exclude responses delayed by longer than 5 minutes from the analyses. Data will be aggregated at the day-to-day level to indicate the following: whether cannabis was used; the total number of joints/grams consumed; mean daily potency; mean daily levels of mental health symptoms, self-efficacy, health-related quality of life, working memory, and impulsivity; whether participants drove while intoxicated; and total amount of physical activity. By using multi-daily records to examine day-level phenomena, we will minimize measurement error related to poor recall and random variability. For the 2-week baseline period and each week of the 6-week experimental period, we will calculate frequency of cannabis use as the number of days used per week. To quantify change in frequency of cannabis use from baseline, change scores will be calculated by subtracting number of days per week of cannabis use during the 2-week baseline from those levels

recorded during each week of the mCM treatment period. A dichotomous variable will also be calculated reflecting whether a given participant achieved at least a 50% reduction in cannabis use during a given week. Thus, the data will be structured such that each participant will have up to 56 rows of data corresponding to each day of the 2-week baseline period and 6-week mCM/non-contingent control. Each row will contain a dichotomous indicator of whether or not cannabis was consumed that day, total quantity of cannabis consumed that day, total THC load of the cannabis used that day, daily estimates of functioning, a baseline estimate of cannabis use, and three variables capturing weekly varying frequency, quantity, and total THC load of cannabis use: the aforementioned dichotomous variable measuring whether a 50% reduction from baseline use was achieved and a change score, with a 0 change-score value for days falling during the 2-week baseline.

E.3. Hypotheses 1a and 1b.

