To examine the effect of reduced cannabis use on functioning assessed with EMA, day-by-day outcome variables will be modeled *via* MLM as a function of treatment group (Level 2), week (Level 1; with the two baseline weeks treated as a single week), and treatment-by-week interactions. Daily consumption (total equivalent number of joints/gram consumed and total potency; Level 1) will be examined as potential covariates. Linear and quadratic time effects will be explored. Week-by-week effects of cannabis reduction will be examined in separate models. We will also examine the effects of reduced use by modeling day-by-day and week-by-week outcomes as a function of week-by-week reductions in cannabis, independent of treatment group. Linear MLM will be used to model normally distributed outcome variables *via* PROC MIXED. Generalized linear MLM will be used to model dichotomous and otherwise non-normally distributed outcome variables *via* PROC GLIMMIX.

E.4. Supplementary Aim.

To examine whether reduced cannabis use moderates or is moderated by other factors (e.g., sex differences), the models examined in Hypotheses 1a and 1b will be modified to include potential Level-1 (e.g., day-to-day craving, sleep) and Level-2 (e.g., sex, baseline cannabis use, self-efficacy) predictors as well as their interactions with week-by-week change in cannabis use. For instance, to determine whether a week-by-week reduction in cannabis use moderates the association of day-by-day cannabis use (or abstinence) with daily working memory, whether or not participants used cannabis that day (Level 1) will be added as a predictor of working memory as will its interaction with week-by-week change in frequency or quantity of cannabis use. This particular model could thus determine whether cannabis users demonstrate greater cognitive functioning on abstinent days when they reduce their cannabis use.

E.5. Power Calculations.

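### Weekly cannabis frequency is a raw count of days used with no denominator of reported days, so unreported days can read as reduced use in the reduction-based models

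*Combined protocol and SAP*

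**What the plan says.** E.2 aggregates diary data to the day and then to the week: "we will calculate frequency of cannabis use as the number of days used per week". The change score subtracts baseline days per week from each treatment week's figure. A yes/no flag marks weeks with at least a 50% reduction. Prompt responses more than 5 minutes late are excluded. E.2 does not say what counts as a reported day, how many are needed in a treatment week, or how a day without a usable report is handled.

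E.1 says "we do anticipate missing values in the EMA data". It relies on maximum likelihood on all available data and, if data are suspected to be missing not at random, says that "multiple imputation will be used to analyze non-random patterns of missing EMA data". No imputation model is given.

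E.3 first models outcomes by treatment group, week and their interaction. It then adds models of outcomes "as a function of week-by-week reductions in cannabis, independent of treatment group". E.4 builds its moderator models on the same weekly change. Hypothesis 1a is worded as an association: "Decreased cannabis use will be associated with significant improvements in mental health symptoms".

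The only completeness threshold for continuing is 10 of 14 nightly diaries (D.6.1), which covers the ad lib period alone.

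**The concern.** A predictor formed by counting use days mixes two things: how often the person used cannabis and how many days they reported. The plan never says that blank days are non-use, but a literal count has that effect. Maximum likelihood deals with missing outcomes; it does not repair a predictor computed from an incomplete week.

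If reporting varies with functioning, the count produces an association between apparent reduction and functioning where none exists. The direction is not known. If people report less in bad weeks, those weeks look like reductions with poor functioning, which masks benefit. The opposite pattern inflates benefit. Hypotheses 1a and 1b are worded as associations with decreased use, which is what the affected models estimate.

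**Working it through.** **The plan's own figure.** E.5 counts 60 x 7 = 420 weekly values and states 90% power for r = .16. Fisher's z gives Phi(atanh(.16) x sqrt(417) - 1.96) = 0.909, so the figure reproduces. It is not in dispute; it takes the weekly change values as given.

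**Arithmetic for a daily user whose use does not change.**
- Baseline 14/14 = 7 per week, treatment week 5/7 reported: 5/7 - 1 = -29%.
- Baseline 10/14 = 5 per week, treatment week 7/7 reported: 7/5 - 1 = +40%.
- Baseline 14/14, treatment week 3/7 reported: 3/7 - 1 = -57%, flag triggered. At 4/7 it is -43%, not triggered.

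Real change is distorted too. The pilot reduction in B.5 is (17.5 - 10.3)/17.5 = 41%. With a complete baseline it reads as 50% once treatment-week reporting falls to 0.5/(10.3/17.5) = 85%.

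**Share of days reported.** No R33 figure is given. The 96% in B.1 (video uploads) and the 87% in D.6.1 (working-memory prompts) come from other studies and are not day-level. D.1 cuts the daily alarms to two, so with the morning and nightly entries there are four entries a day. If each were completed independently with probability 0.87, 1 - 0.87 = 13% of days would lack the nightly report, but only 0.13^4 = 0.03% would be wholly blank. Reported days therefore run from 87% to 99.97% depending on a definition that the plan omits. Real misses may cluster.

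**False-positive rate of the reduction model.** Simulated null trials used these settings:
- 60 people, a baseline plus six treatment weeks, intraclass correlation 0.5, and no effect of use on outcome.
- Baselines screened at 10 or more of 14 days; equal reporting in both phases.
- Reporting linked to functioning at 0.3 log-odds per SD (assumed).
- Random-intercept model of weekly outcome on the change score plus week effects. The rate needs at least 4 of 7 days.
- Baseline use 58% of days (17.5/30, B.5) or 85% (assumed; no source in the documents).
- About two thirds of people truly reduce, by 18-93%. The range is the pilot's (B.5); applying it this way is an assumption.

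| Days reported | Count, 58% use | Count, 85% use | Rate |
|---|---|---|---|
| 87% | about 14-15% | about 22% | near 5% |
| 96-99% | about 4-7% | about 4-7% | near 5% |

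If instead nobody changes use, the count gives 26-28% (58% use) and 63-67% (85% use) at 87% reported. With nobody changing use and no link between reporting and functioning, it gives 4-7%.

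**The 50% flag, nobody changing use, 87% of days reported.** False flags per person-week, count against rate, are 20% v 17% at 44% use (the eligibility floor, 40/90), 13% v 10% at 58%, and 3% v 1% at 85%. With full reporting they are already about 16%, 9% and 0.8%, from comparing a 7-day week with a 14-day baseline.

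**Limit of the rate.** Suppose there are 5 true use days, with 50% of use days and 90% of the other two days reported. The count is 5 x 0.5 = 2.5. The rate is 7 x 2.5/(2.5 + 2 x 0.9) = 4.07. It is closer to 5 but still biased.

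**The case against.** The best defence is that blank days should be rare. Use is asked at every entry and again each night for the past 24 hours, missed alarms are re-prompted (D.6.1), and D.4 pays a "bonus per week for not missing more than 1 EMA alarm per day". Losing 13% of days requires the nightly report to be the only valid source, which the plan does not say. This stands as a limit on size: at 96-99% of days reported the count is close to nominal. It does not supply a derivation rule. The R21 adherence standard of "1 or more EMA assessments per day" (C.6.5) does not either: it is a feasibility milestone, and a single morning entry meets it while missing later use.

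A second defence is that the plan is silent rather than wrong. E.2 allows up to 56 rows per person, so blank days may simply be absent rows, and imputing daily use before counting would be consistent with E.1. Both readings are permissible, but neither is stated, and a count over absent rows still comes out low.

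A reader might infer false-positive rates of 26-67%. Those need every participant to keep use unchanged, in a trial whose intervention is meant to reduce it, together with the assumed 87% of days reported; the upper end also needs the 85% use level. A reader might also infer that the multiple-imputation sentence in E.1 is an error. Imputation can be carried out under a missing-not-at-random model; the gap is that no model is specified, and the standard form assumes missing at random.

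**Conclusion.** The concern holds in a limited form. The stated derivation lets incomplete reporting pass as reduced use, and no other section corrects this. It bears on the E.3 reduction models, the 50% flag and the E.4 moderator models. It should not be read as undermining the randomised group-by-week models, which use group and week rather than this count, or the 60 x 7 count in E.5.

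Under the assumed link and assumed true reductions, inflation is material at 87% of days reported (about 14-22% against a nominal 5%, the upper figure resting on the assumed 85% use) and small at 96-99%. Neither the true reporting rate nor the link can be read from the documents, so the trial may sit anywhere in that range. The effect on the flag is modest: at 44-58% use most false flags are 7-day sampling noise, which a denominator does not remove. The rule should be fixed before analysis.

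**What to change.** 1. Define weekly frequency as 7 x (use days / usable days) in both phases. A usable day has the nightly 24-hour report, or otherwise complete use entries from sources present in both phases. A day known only from an ad lib self-initiated reading (D.6) should not qualify. Late prompt responses are already excluded; state how re-prompted and nightly entries are treated.
2. Set weeks below a prespecified minimum, for example 4 of 7 usable days, to missing. Apply the same rule to the 50% flag, and report usable days per week by group.
3. Specify the model behind the multiple-imputation sentence in E.1: a delta-adjusted sensitivity analysis that imputes blank days over a stated range, including missing day = use day. The cannabis Timeline Followback re-administered at follow-up (Table 3) can support it. Saliva results help less, because the tests run with the same alarms (C.6.2).

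Cost: SAP wording, derivation code and sensitivity analysis on data already planned for collection. With the 4-of-7 minimum, about 1% of person-weeks become missing at 87% reporting and about 14% at 70%. (Independent days alone give 0.7% and 12.6%; the link to functioning adds the rest.) Timeline Followback relies on recall and is absent for people lost before follow-up, so it should remain a supporting source.

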Eligible participants will be trained in the EMA procedures following established procedures at the end of the baseline assessment (Beckham, Calhoun 2013). Participants will then practice with the electronic diary at home for 24 hours. Once the training period is complete, participants will complete an 8-week EMA study in which they will carry the diaries with them on a daily basis. The first 2 weeks of the EMA study will involve daily assessments of cannabis use and participants' functional outcomes during the *ad lib* period to establish baseline patterns of use. During the *ad lib* period, participants will also be asked to perform self-initiated diary readings when they begin cannabis use. When participants begin the diary reading, the phone will set an alarm for 60 minutes later. When the alarm sounds, the participant will use a saliva test kit and upload the readings. Participants will be paid \$5 once per day if they begin a self-initiated reading on that day. On day 15, participants in the Reduced Use Condition ($n = 48$) will begin reducing their cannabis use through participation in the mobile CM for cannabis protocol, whereas participants in the Control Condition ($n = 24$) will receive non-contingent payments based on the mean of two yoked participants' earnings. All participants will continue to provide EMA assessments of their functional outcomes during the 6-week experimental period so that we can study the impact of reduced cannabis use on functioning. Electronic diary data stored on the smart phone are encrypted at rest. Data will be downloaded from the smart phones to duhsnas-pri\dusom_psych\private\irb\[name]\Marijuana.

Table 3. Description and Timing of In-Person Assessments

| MEASURE | DESCRIPTION | BL | End of ad lib | 8-wk |
|--|---|----|----------------------|------|
| Demographic Assessment | PhenX (Hamilton et al., 2011) protocols will assess age (#010101), race (#010601), ethnicity (#010501), gender (#010700), and sexual orientation (#101401). | X | | |
| Structured Clinical Interview for DSM-5 (First et al., 2015) | Will be used to diagnose CUD and other psychiatric disorders based on DSM-5 criteria in order to determine study eligibility and characterize sample. | X | | |
| Columbia Suicide Severity Rating Scale (Posner et al., 2011) | State-of-the-art interview that assesses the full continuum of suicidal behavior. Will be used to determine study eligibility and assess suicidal behavior. | X | | X |

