Power calculations are based on Hypotheses 1a and 1b and were performed with Power Analysis and Sample Size software (PASS, Version 12: NCSS LLC, Kaysville, Utah). We conservatively estimate that as many as 12 participants could potentially need to be excluded due to sustained abstinence, leaving a minimum of 60 participants available for analysis. The corresponding analyses make use of multilevel data with a total sample of up to 3,360 records (60 participants X 56 daily observations). Because there will only be 7 unique estimates per participant of week-to week change in frequency of cannabis use, a conservative minimum estimate of the effective sample size is 420 (60 participants X 7 weekly

observations). Although these observations are non-independent given clustering within participants, hence the use of MLM, accounting for variation between participants will reduce the error variance in the dependent variables. Thus, the effective sample size will very likely exceed 420. An effective sample size of 420 has 90% power to detect small-to-medium treatment effects equivalent to Cohen's $d = 0.30$ or associations equivalent to $r = .16$.

References

Adkisson, K., Cunningham, K.C., Dedert, E.A., Dennis, M.F., Calhoun, P.S., Elbogen, E.B., Beckham, J.C., & Kimbrel, N.A. (manuscript under review). Cannabis use disorder and post-deployment suicide attempts in Iraq/Afghanistan-era veterans.

Babor TF, de la Fuente JR, et al., 1989. AUDIT The Alcohol Use Disorders Identification Test: Guidelines for use in primary health care (WHO/MNH/DAT 89.4). Geneva, Switzerland.

Beckham, J.C., Adkisson, K.A., Hertzberg, J., Kimbrel, N.A., Budney, A.J., Stephens, R.S., Moore, S.D., & Calhoun, P.S. (manuscript under review). Mobile contingency management as an adjunctive treatment for co-morbid cannabis use disorder and cigarette smoking.

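### E.3 lets each randomised arm keep its own ad lib mean and plans no baseline-outcome adjustment; a common ad lib mean would be a cheap gain in precision, secure only in the all-randomised set.

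*Combined protocol and SAP*

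**What the plan says.** The trial is randomised: "Seventy-two participants will be randomized using a 2:1 allocation ratio", 48 to Reduced Use and 24 to Control (D.1). On the ad lib phase, D.6 says: "The first 2 weeks of the EMA study will involve daily assessments of cannabis use", and of functional outcomes too. The arms' procedures diverge on day 15. E.2 lays the data out as up to 56 daily rows per participant, that is 14 ad lib and 42 experimental days.

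For the main comparison, E.3 begins: "To examine the effect of reduced cannabis use on functioning assessed with EMA, day-by-day outcome variables will be modeled". The predictors are treatment group, week with the two ad lib weeks merged into one level, and their interaction. Linear and quadratic time are to be explored as well. A second family of models relates outcomes to weekly reductions in use, without regard to arm.

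No baseline value of the functional outcome enters the main model. The baseline item in the E.2 data rows is cannabis use, not functioning. E.1 adds baseline variables only if they turn out to be related to missingness, and E.4 adds baseline terms only to study moderation. E.3 does not state the random-effects structure, whether week is categorical, or which interaction contrast is decisive.

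D.2 removes participants whose saliva tests are all negative in the six experimental weeks. It allows for up to 12 of 72, and E.5 plans on the remaining 60.

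**The concern.** A group main effect beside a categorical week factor that includes the ad lib level gives each arm a free ad lib mean. Each group-by-week coefficient is then a difference in differences: the arm difference in that week minus the entire arm difference in the ad lib period. If the arms are formed by randomisation and treated alike until day 15, their expected ad lib means are equal and the observed difference is noise. Subtracting all of it adds variance unless ad lib and later levels are so closely related that full subtraction is already optimal.

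With 60 to 72 participants and about 20 to 24 controls, precision is scarce. Fixing the baseline handling in advance also prevents a later choice between change-type and adjusted estimates.

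**Working it through.** **The plan's own figure.** E.5 claims 90% power from an effective sample of 420 (60 x 7) at two-sided alpha .05. For r = .16 this reproduces (.909). For d = 0.30 it does not: .867 with a 1:1 split, .826 with 2:1. That is a separate matter. E.5 uses neither the E.3 contrast nor any baseline correlation, so no stated figure changes here.

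**Formulas.** Let Vb and Vp be the between-person variances of the ad lib mean and the experimental-period mean of a linear outcome, and C their covariance.

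- Planned contrast, variance per person: Vb + Vp - 2C.
- Common ad lib mean: Vp - C²/Vb.
- Difference: (Vb - C)²/Vb, which is never negative.
- With Vb = Vp and correlation r, the proportional saving is (1 - r)²/[2(1 - r)] = (1 - r)/2: 25% at r = .50, 15% at .70, 10% at .80, 5% at .90.

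The proportion does not depend on allocation; 48/24, 40/20 and 36/24 give the same value.

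**With 14 and 42 days.** From the documents: the numbers of days. Assumed: total daily variance 1, lag-1 autocorrelation 0.3 within person, ICC 0.3-0.7, and correlation 0.6-1.0 between a person's true ad lib and true experimental-period levels. The variance factor of a mean of n daily residuals is [n + 2 Σ(n - k)0.3^k]/n², with k from 1 to n - 1. It is 0.1264 for n = 14 and 0.0435 for n = 42.

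Example, ICC 0.5 and true-level correlation 0.8:

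- Vb = 0.5 + 0.5 x 0.1264 = 0.563; Vp = 0.5 + 0.5 x 0.0435 = 0.522; C = 0.8 x 0.5 = 0.400.
- Planned: 0.563 + 0.522 - 0.800 = 0.285.
- Common mean: 0.522 - 0.160/0.563 = 0.238.
- Saving 16.6%, equivalent to 60/(1 - 0.166) = about 72 participants instead of 60.

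| ICC | True-level correlation | Saving |
|---|---|---|
| 0.3 | 0.6 | 31% |
| 0.5 | 0.7 | 21% |
| 0.5 | 0.9 | 12% |
| 0.5 | 1.0 | 8% |
| 0.7 | 1.0 | 4% |

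**Other covariance structures.** Exact generalised least squares on the 56-day layout:

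| Structure (assumed) | Six-week average | Last week | Linear slope |
|---|---|---|---|
| Random intercept, ICC 0.3 | 10.7% | 4.8% | 5.8% |
| Random intercept, ICC 0.5 | 5.0% | 2.2% | 2.6% |
| Random intercept, ICC 0.7 | 2.2% | 1.0% | 1.2% |
| Random intercept and slope | 1.4-3.3% | 0.5-1.3% | 0.4-1.3% |

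A random intercept with ICC 0.2 gives 16.7% for the six-week average. Adding week-level or autoregressive person variation gives about 6-43%.

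**Power, for scale.** With 40/20 analysed, d = 0.30 and equal variances, power is Φ(0.30/√[v(1/40 + 1/20)] - 1.96), with v = 2(1 - r) as planned and v = 1 - r² with a common mean. At r = .58 it rises from .222 to .269; at r = .76, from .352 to .392.

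**The D.2 exclusion.** Suppose all 12 exclusions come from the 48 in Reduced Use, leaving 36 against 24, and the excluded participants' ad lib level is better by δ SD. The analysed arm's baseline mean shifts by δ x 12/36, and the constrained estimate moves by (1 - r) times that, relative to the change contrast.

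| δ | Shift (SD) | Bias, r = .58 | Bias, r = .76 | MSE, constrained/planned |
|---|---|---|---|---|
| 0.25 | 0.083 | 0.035 | 0.020 | 0.81 / 0.89 |
| 0.50 | 0.167 | 0.070 | 0.040 | 0.87 / 0.93 |
| 0.80 | 0.267 | 0.112 | 0.064 | 1.00 / 1.00 |

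The last column gives r = .58, then r = .76. At 0.8 SD the whole gain is gone.

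**The case against.** The planned model is a standard one and, in all randomised participants, is not biased by its free baseline means. This is a matter of efficiency, not an error. That stands and sets the weight of the point.

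Three further objections limit it.

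- **Equal baseline means.** D.2 selects participants on a result that arises after randomisation and is likely to occur mainly in the arm paid for abstinence. The analysed arms then need not share an ad lib mean, and the constraint can trade variance for bias. This stands. The bias shown above is, however, measured against the change contrast, which the same exclusion can also distort.
- **Timing of allocation.** The text does not say whether randomisation precedes the ad lib period. The design figure is not available, so this cannot be called an omission. Until it is confirmed, the absence of any arm effect before day 15 is partly an assumption.
- **Size.** The documents give no ICC, autocorrelation or baseline-to-follow-up correlation. If a person's true level hardly moves, full subtraction is nearly optimal and little is gained.

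A reader might infer that the adjustment costs nothing in any analysis set, or that 12-21% (the values at ICC 0.5 with true-level correlation 0.9-0.7) is the expected saving. The documents support neither: the first fails under D.2, and the second rests wholly on assumed inputs. Nor do the percentages carry over directly to linear-slope contrasts, to the GLIMMIX outcomes, or to the models that ignore treatment group, where a common arm mean has no role.

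**Conclusion.** The point holds as a cheap improvement. With week categorical, E.3 subtracts the full chance ad lib difference from every treatment-by-week contrast, and nothing elsewhere in the plan adjusts for the ad lib value of the outcome. Given truly equal baseline means, a common mean cannot raise the variance of a linear contrast when the covariance structure is correctly specified. The saving may be material (about 4-31% over the assumed grid) or slight (about 0.4-11% under plain random-intercept models with ICC 0.3-0.7 and the random-slope models examined). The price is reliance on equal ad lib means, which randomisation secures only when all randomised participants are analysed and ad lib behaviour and reports cannot be influenced by knowledge of the arm.

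**What to change.** For the randomised-arm comparison in E.3:

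1. State that week is categorical in the main model, and prespecify one ad lib mean common to both arms, with arm-specific means only for the six experimental weeks. Alternatively, analyse the experimental days with each participant's ad lib mean of the same outcome as a covariate. The two are close but not identical when diaries are incomplete or the link is non-linear, so name one as primary.
2. Run it in all randomised participants, and state that allocation is made or disclosed only after the ad lib period. Say also where the D.6.1 withdrawal for too few nightly diaries falls relative to randomisation.
3. If an analysis keeps the D.2 exclusion, do not impose the common mean there without a sensitivity analysis using the unconstrained model.
4. State the covariance structure and give the expected saving as a range over stated r, not as a single figure.

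The cost is a few sentences in E.3 and a small change of model code, with no new data collection. The larger decision is to define an all-randomised analysis set alongside the one in D.2.
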